- Current use of oral lopinavir/ritonavir solution (and the inability to switch to a solid dosage form during the entire duration of the study).
- Current use of warfarin.
- ALT or AST > 2 x the upper limit of normal or total bilirubin outside the normal range.

	
 • Creatinine clearance (CrCl) < 50 mL/min by Cockcroft-Gault. • Allergy to rubber or thiuram derivatives
TEST PRODUCT, DOSE, AND ROUTE OF ADMINISTRATION	
Oral disulfiram given as 1000 mg daily (cohort 1) or 2000 mg daily (cohort 2) versus placebo for 5 consecutive days in adults with early symptomatic SARS-CoV-2 infection will be administered in a double-blind fashion.
 
Placebo tablets will be administered in a double-blind fashion and given as a single oral administration on days 1-5.

DURATION OF PARTICIPATION AND DURATION OF STUDY	
Study products will be administered at days 1-5. Participants will be observed on study at days 5, 15, and 31.
 
Participants will be randomized to either of two treatment arms, oral disulfiram or placebo.
 
Screening: up to 7 days prior to treatment randomization.
 
Treatment (for each arm): 5 days (participants to be observed for a total of 4 hours on the last treatment day, Day 5)
 
Follow-up (for each arm): 31 days after the initial dose for that treatment arm.
 
The total duration of the study is expected to be 31 days (approximately 1 month).

CONCOMITANT MEDICATIONS	
The following medications are not allowed during the study because of potential interactions with disulfiram: warfarin; any over the counter drug, food or other product that contains or might contain alcohol; if HIV-positive, specific protease inhibitor preparations (oral amprenavir solution, ritonavir solution, lopinavir/ritonavir solution, soft gelatin form of ritonavir or lopinavir/ritonavir, tipranavir).

EFFICACY EVALUATIONS	
 • Change in plasma inflammatory biomarker levels² • Change in SARS-CoV-2 viral load⁴ • Change in COVID-19 symptom severity³ (5-point scale)
PRIMARY ENDPOINTS	
 • Change in plasma inflammatory biomarker levels² (e.g., IL-6, IL-1β) at days 5, 15, and 31.

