5.5.2 Study Drug/ Placebo Administration (Day 1)

5.5.2.1 Pre-Dose (Between Hour -0.5 and 0)

1. Questionnaire Evaluation to include the Index Follow up Questionnaire
2. Targeted physical exam and vital signs
3. Clinical lab collection

4. Samples collected for research (storage)
 - a. Blood: PBMC (CyTOF, single cell sequencing), plasma (plasma SARS-CoV-2 viral load), serum (SARS-CoV-2 serology)
 - b. Nasopharyngeal swab for SARS-CoV-2 viral load
 - c. Saliva for host DNA sequencing and potential future SARS-CoV-2 quantification (RNA levels and anti-SARS-CoV-2 IgA)

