5.5.3 Study Drug/ Placebo Administration (Day 2)

Participant will come to the clinic for clinical laboratory to include complete blood count with differential, urea, electrolytes, creatinine, calcium, magnesium, phosphate, liver function tests, erythrocyte sedimentation rate (ESR), high sensitivity C-reactive protein (hs-CRP), D-dimer, lactate dehydrogenase (LDH), and ferritin, plasma PK testing, and Nasopharyngeal swab for SARS-CoV-2 viral load. Saliva for host DNA sequencing and potential future SARS-CoV-2 quantification (RNA levels and anti-SARS-CoV-2 IgA) will be collected.

The participant will be asked to hold the day 2 study medication until after the blood draw. After the blood has been collected, the participant will be asked to take their day 2 dose of study medication. The time of pre-dose blood draw and the study medication administration date and time will be recorded.

The subject will complete a daily symptom check using the COVID-19 symptom severity questions adapted from the Somatic Symptom Scale (SSS-8) (table 3) while at the clinic and will be assessed for any adverse events.

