5.5.4 Study Drug/ Placebo Administration (Day 3)

Participant will self-administer the third dose of disulfiram or placebo at home. The participant will note the time of self-administration and will complete a daily symptom diary. Study coordinator will call patient to verify their symptoms, confirm self-administered dose, and evaluate for any adverse events. If any AEs are reported, an AE form will be completed by the study coordinator, and the PI will be notified for any Grade 3 or above AE.

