5.5.11 Follow-Up (Day 31)

5. Questionnaire Evaluation
6. Targeted physical exam and vital signs
7. Clinical lab collection
 - a. Complete blood count with differential, urea, electrolytes, creatinine, calcium, magnesium, phosphate, liver function tests, erythrocyte sedimentation rate (ESR), high sensitivity C-reactive protein (hs-CRP), D-dimer, lactate dehydrogenase (LDH), and ferritin.
8. Samples collected for research (storage)
 - a. Blood: PBMC (CyTOF, single cell sequencing), plasma (plasma SARS-CoV-2 viral load), serum (SARS-CoV-2 serology)
 - b. Nasopharyngeal swab for SARS-CoV-2 viral load
 - c. Saliva for host DNA sequencing and potential future SARS-CoV-2 quantification (RNA levels and anti-SARS-CoV-2 IgA)
 - d. HIV+ participants: a CD4+/CD8+ T cell count and standard plasma HIV RNA assay.
9. Samples collected for research (storage)
 - a. Blood: PBMC (CyTOF, single cell sequencing), plasma (plasma SARS-CoV-2 viral load), serum (SARS-CoV-2 serology)
 - b. Nasopharyngeal swab for SARS-CoV-2 viral load

- c. Saliva for host DNA sequencing and potential future SARS-CoV-2 quantification (RNA levels and anti-SARS-CoV-2 IgA)

5.6 Table 3. COVID-19 symptom severity questions adapted from the Somatic Symptom Scale (SSS-8). 3

Symptom	New occurrence or worsening of pre-existing symptom during illness	When did it start? (MMM/DD/YY) If day cannot be estimated within 3 days of true onset, include month and year and mark day not known.	Skip if start date known. Was it present in the first 3 days of illness?	Are you still experiencing it, meaning in the past 2 days? For recovered phase, add: By this we mean that your initial symptoms you had when you first developed COVID-19 have not gone away.	Skip if still experiencing the symptom. How many days did it last? This is defined as start date to last date experienced.	When the symptom was at its worst, how much did it bother you? Please answer on a scale from 1 to 5, where 1 is NONE and 5 is VERY MUCH.
Feeling feverish	 Yes  No	____/____/____  Day not known	 Yes  DK  No	 Yes  No	 Don't know	 1  3  5  2  4

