From the time to treatment initiation to clinical recovery or improvement, all participants will be censored at the end of follow-up, not at the time of event (e.g., for mortality). Sensitivity analyses will be performed using imputation of missing data to differentiate discontinuation of participants from treatment versus study evaluations.

Duration of fever, duration of symptoms and duration of time to self-reported return to usual health will be summarized with descriptive statistics. Participant-specific durations of fever and symptoms will be compared between study arms using a two-sided stratified Wilcoxon test with a 5% Type I error rate. Total symptom score will be calculated on each day and the participant-specific area under the curve (AUC) over time will also be compared using a two-sided stratified Wilcoxon test. Participants who do not have complete diary cards due to hospitalization or death will be ranked in these analyses as having poorer outcomes than participants who survived without hospitalization.

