6.2.1 Primary endpoint

- Changes in plasma inflammatory biomarker levels² (e.g., IL-6, IL-1 β) at days 5, 15, and 31.

6.2.2 Secondary endpoint(s):

- Safety and tolerability (frequency of Grade 2 or higher adverse events) at days 2, 3, 4, 5, 7, 9, 11, 15, and 31.
- Change in SARS-CoV-2 PCR quantitative viral load⁴ at days 5, 15, and 31.
- Change in COVID-19 clinical stage (five-point symptom severity scale³) at days 5, 15, and 31.
- The proportion of detectable versus not detectable levels of SARS-CoV-2 RNA from site-collected NP swabs at entry, day 5, and day 15 among a subset of participants.

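### The only 1–5 symptom rating shown asks about each symptom at its worst, with no recall window and no scoring rule, so the repeated score may miss easing of symptoms

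*Combined protocol and SAP*

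**What the plan says.** **The instrument.** Table 3 in section 5.6 lists 26 symptoms plus two free-text rows. Its only graded item asks "When the symptom was at its worst, how much did it bother you", answered from 1 (none) to 5 (very much). No period is attached, and the opening column of each row refers to the illness as a whole. The one short window in the table belongs to a separate yes/no item: "Are you still experiencing it, meaning in the past 2 days".

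**Its repeated use.** On Day 2 (section 5.5.3) the participant completes a "daily symptom check using the COVID-19 symptom severity questions adapted from the Somatic Symptom Scale (SSS-8) (table 3"). At Days 3 and 4 the participant "will complete a daily symptom diary" (wording from section 5.5.4), and similar diaries follow in sections 5.5.7 to 5.5.9. The Day 1 visit has a "Questionnaire Evaluation to include the Index Follow up Questionnaire" (section 5.5.2.1). Neither the diary nor that questionnaire is reproduced.

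**The analysis.** The synopsis lists "Change in COVID-19 symptom severity" as an efficacy evaluation. Section 6.2.2 lists "Change in COVID-19 clinical stage (five-point symptom severity scale") at days 5, 15 and 31 as a secondary endpoint. Section 6.2 adds: "Total symptom score will be calculated on each day and the participant-specific area under the curve (AUC) over time will also be compared", by a stratified Wilcoxon test. Section 5.1.2 identifies the scale as the adapted SSS-8, and the synopsis and section 6.2.2 cite the same reference for it.

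**The concern.** A change from baseline and a daily AUC need severity at a point in time. A question about the worst point of an illness is a history question. Repeated literally, its answer can rise but never fall. If those answers are summed, a patient who recovers quickly scores like one who recovers slowly.

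The yes/no item could be used to drop a symptom once it has gone, but no section says that it will be. Even then, a symptom that has eased and not gone keeps its peak score. The documents also do not say which symptoms enter the total, what a resolved symptom scores, or how item ratings become one five-point stage.

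At stake are the symptom-change endpoint and the AUC comparison. Unlike a gap in the analysis text, this one cannot be repaired after data collection.

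**Working it through.** The documents give no power or effect size for the symptom endpoint, so there is no stated figure to reproduce. The check compares three ways of scoring the same illness. All symptom courses below are assumed.

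**Definitions.** For one symptom on day *t*:
- current rating *c(t)*, from 1 (absent) to 5;
- worst-ever rating *W(t)* = the maximum of *c* up to day *t*;
- gated rating *G(t)* = *W(t)* while the symptom is still present, and 1 once it is absent (the 2-day look-back is ignored).

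AUC is by the trapezoid rule over days 1–31. A constant rating of 1 contributes 1 × 30 = 30.

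**Change.** Let *c* = 4 on Day 1, easing linearly to 1 over 10 days. On Day 5, *c* = 4 − 3 × 4/10 = 2.8.

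| Scoring | Day 5 | Day 15 | Day 31 |
|---|---|---|---|
| Current | −1.2 | −3 | −3 |
| Gated | 0 | −3 | −3 |
| Worst-ever | 0 | 0 | 0 |

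**AUC, recovery in 6 versus 10 days.**
- Current: 30 + ½ × 3 × 6 = 39.0, against 30 + ½ × 3 × 10 = 45.0.
- Gated (stays at 4, then drops to 1 on the last day): 30 + 3 × 5 + 1.5 = 46.5, against 30 + 3 × 9 + 1.5 = 58.5.
- Worst-ever: 4 × 30 = 120 for both.

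**AUC, same resolution day, different easing.** Both patients start at 4 and are symptom-free on Day 15. One is at 2 on days 2 to 14. The other eases linearly.
- Current: 30 + 2 + 12 + 0.5 = 44.5, against 30 + ½ × 3 × 14 = 51.0.
- Gated: 30 + 3 × 13 + 1.5 = 70.5 for both.
- Worst-ever: 120 for both.

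**Whole-number ratings at contact days** (1, 2, 3, 4, 5, 7, 9, 15, 31). A fast course of 4, 4, 3, 2, 2, 1, 1, 1, 1 changes by −2, −3, −3 at days 5, 15 and 31, with AUC 39.0. A slow course of 4, 4, 4, 4, 3, 3, 2, 2, 1 changes by −1, −2, −3, with AUC 62.5. On the worst-ever reading both change by 0, 0, 0 and both have AUC 120.0.

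**Power of the AUC comparison, for direction only.** Simulated with 8 symptoms per patient, peaks of 2–5, an unstratified two-sided Wilcoxon test and AUC over days 1–31. The sizes are 20 versus 10 (one cohort) and, in brackets, 40 versus 20 (both cohorts pooled).

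| Assumed treatment effect | Current | Gated | Worst-ever |
|---|---|---|---|
| A. Faster resolution (mean 6 or 7 vs 10 days) | 32–57% (53–87%) | 30–55% (52–82%) | 3–5% (3–6%) |
| B. Easing only, same resolution dates | 18–28% (34–55%) | 4% (4–5%) | 4% (5–6%) |
| C. Less worsening only | 6–12% (6–20%) | 6–9% (6–13%) | 8–32% (12–64%) |

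In A, 0, 25 or 50% of symptoms peak after Day 1. In B, the excess over 1 is multiplied by 0.4 or 0.6 in the treated arm. In C, 15% vs 30%, or 20% vs 60%, of symptoms worsen by 1 point for 3 days. A used 600 trials per setting; B and C used 1,000. Monte Carlo error is about 3–4 points. With no treatment effect (20 vs 10), rejection was 5% current, 5% gated and 6% worst-ever.

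A second simulation on different assumed courses (300 trials per setting, 20 vs 10) gave the following:
- Faster resolution: 37–57% current, 36–58% gated, 4–5% worst-ever.
- Easing only: 51–90% current, 3–6% for the other two scorings.

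The absolute power for easing moved a great deal between the two simulations; the ordering did not.

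**The case against.** The strongest reply is that the repeat forms are not shown. Table 3 looks like part of a longer illness-history interview: it points to question numbers outside itself and has a variant for the recovered phase. Only the Day 2 check is tied to it by name, and Day 2 is not a change time point. The diary may carry its own recall period. A participant filling in a daily diary may in any case answer for that day, and section 5.1.2 says the scale follows FDA guidance on outpatient symptoms. This stands as a limit on certainty: the score may miss easing; it is not shown that it will. It does not remove the point, because the only wording given is worst-ever, and mixed readings would add noise.

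A second reply is that the link from Table 3 to the clinical-stage endpoint is inferred. It is closer than that, since section 5.1.2 names the adapted SSS-8 and the endpoint lists cite the same reference. How ratings become a single stage is still undefined.

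Third, the power figures rest on invented inputs: 8 symptoms rather than 26, no stratification, and an AUC window that section 6.2 does not state. That is correct, and they show direction only.

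Last, the study calls itself exploratory, these endpoints are secondary, and time to recovery and the symptom and fever durations do not use this rating. All of that stands and limits the weight of the point.

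**Conclusion.** The concern holds. As written, the only graded symptom item cannot fall on repeat, while the endpoints built on the scale need it to. Summed as worst-ever, the change and AUC are largely blind to recovery (120 versus 120 where a current rating gives 39.0 versus 45.0). Gated by the yes/no item, they see resolution but not easing (70.5 versus 70.5 where a current rating gives 44.5 versus 51.0). Less new or further worsening after baseline would still register on the worst-ever item.

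This rests on participants answering the item literally and on the repeat forms matching Table 3, neither of which the documents settle. Confidence is therefore medium. The primary biomarker endpoint and the duration outcomes are unaffected. It should be fixed because the lost information cannot be recovered and the repair is cheap.

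**What to change.** Keep the worst-ever item for illness history. At baseline and at every repeat (diary and visits through Day 31), also ask the same 1–5 question about the past 24 hours, with 1 for an absent symptom. State in section 6.2 that the total score, its change and its AUC use this current rating. In the same place, list the symptoms in the total, give the AUC window, and define how ratings become the five-point stage. If the diary already asks about current severity, reproducing it and naming it as the scored item would settle the wording question.

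The cost is one question stem on the diary and case report form and a short addition to section 6.2. For participants it means one more rating per symptom, so up to 26 plus the free-text rows at each administration, which is a real burden during acute illness. The current rating is also less sensitive than the worst-ever item to brief worsening (pattern C), which is the reason to keep both.

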6 STATISTICAL PLAN

6.1 Sample Size and Power Considerations

Based on a design with 20 patients per disulfiram treatment group within each dosing cohort (1000 mg, 2000 mg) and a null hypothesis that there will be a differential change in plasma inflammatory cytokine levels (e.g., IL-6) in both groups (disulfiram treatment and placebo compared to baseline), we use reported ranges of plasma IL-6 levels in COVID-19 disease¹¹⁹ to estimate sample size and power. Based on a mean plasma IL-6 level of 36.7 pg/mL (95% CI 21.6-62.3 pg/mL), we estimate that the study will have approximately 80% power to detect a 35% difference in plasma IL-6 levels between the disulfiram versus placebo groups. These measurements will be assessed at day 5, 15 and 31 at the 0.05 significance level using a log-likelihood ratio test and non-linear mixed effect regression modeling. This estimate is based on the assumptions that plasma IL-6 levels are log normally distributed and that the standard deviation of the pre- and post-dose levels is 12 ng/mL (derived from ref: DE Leisman et al. Cytokine elevation in severe and critical COVID-19: a rapid systematic review, meta-analysis, and comparison with other inflammatory syndromes). The adjustments will be made for pre-treatment plasma inflammatory cytokine (e.g., IL-6) levels. Safety endpoints will include the total number of Grade 2 or higher events; the number of Grade 2 or higher events possibly, probably or definitely related to study drug; the number of serious adverse events; and the number and cause for treatment or study discontinuation.

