5.3.4 Treatment

A total of 60 participants will be randomized (2:1) to receive active drug versus placebo in a dose escalation study. The first 30 participants will be enrolled in the 1000 mg dosing cohort, randomized 2:1 to receive either disulfiram 1000 mg (N=20) or placebo (N=10) daily for 5 consecutive days. As long as safety monitoring criteria are met to proceed to the second dose, the next 30 participants will be enrolled in the 2000 mg dosing cohort, randomized 2:1 to receive either disulfiram 2000 mg (N=20) or placebo (N=10) daily for 5 consecutive days.

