6.2 Statistical Analysis

All main analyses will be conducted on an intention-to-treat basis. Models will assess the relationship between the timing of disulfiram treatment initiation relative to symptom onset and study outcomes for key efficacy/activity endpoints. The model will be fitted using generalized estimating equations (GEE) to handle the repeated measurements, where the comparison between randomized arms will use a two-sided Wald test. Levels of plasma inflammatory biomarker levels will be compared between arms using non-parametric Wilcoxon rank-sum tests (e.g., separately on days 5 and 15) considering results below the assay limit as the lowest rank. For the analysis of the SARS-CoV-2 viral loads, for the comparison of the proportion of participants with detectable SARS-CoV-2 RNA, we will use binary regression, with adjustment for risk stratum and pre-treatment SARS-CoV-2 RNA level.

For longitudinal analyses, we will perform both statistical summaries at each time point and comprehensive regression modeling. For the regression model, a full non-linear mixed effects (NMLE) model will be developed for disulfiram including all 60 participants across the 5 dosing days. The pharmacokinetics of disulfiram and the measured metabolites will be described by compartmental models parameterized in terms of clearance from the central compartment, apparent central and peripheral Vd and intercompartmental clearance. This will be followed by a full covariate screening process and then inclusion into the pharmacokinetic model. This may include covariates like drug interactions due to other therapy, weight, sex and other biologically plausible covariates collected during the study. From the final model, we will provide the AUC₀₋₇₂, C_{min}, and C_{max} for each patient.

For the primary pharmacodynamics response (plasma inflammatory biomarker levels – e.g., IL-6) the PK and PD data will be combined and analyzed simultaneously by nonlinear mixed-effects modelling (NONMEM version 7.1, Globomax LLC, Hanover, PA). Data will be analyzed using the first-order conditional estimation method with interaction, and ADVAN6 will be used to solve the differential

equations. Both empiric and mechanistic based pharmacodynamics models will be evaluated to describe the concentration effect relationship with the primary pharmacodynamics response.

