Model selection will be based on visual inspection of diagnostic scatter plots, the objective function value (OBJ) computed by NONMEM and biological plausibility of parameter estimates. All final models will be evaluated by performing a visual predictive check (VPC). For this, 1000 data sets will be simulated from the final parameter estimates using the original data as a template. This approach has been successfully applied for the development of animal and human models. From the final model, Monte-Carlo simulations will be undertaken to evaluate if different dosing schedules (e.g. larger doses less often or a single dose) can optimize the dose-concentration-effect relationship.

As this is an exploratory study, we will collect all possible trial outcomes, including those for participants who discontinue treatment. We will attempt to minimize the amount of missing data as much as possible to avoid bias in the interpretability of the findings. However, in the event that missing data is present we will follow standardized methods for handling these data. For time dependent covariates, if one covariate value of a participant is available, this will be carried forward unless the first value of the covariate is missing, then it will be carried backward to occasions with missing values of the respective covariate. The population median value at each time point will be used for missing data from a continuous variable (e.g. age and weight) for a particular participant. If a covariate, which can be classified as a categorical variable (e.g. sex and race), is recorded missing, the observation will be set to the mode. If either race or sex is found significant and there is missing data of the covariate in question in more than 10% of the population, then a sensitivity analysis will be performed, re-estimating the model with and without the covariate only in the participants that have information of the covariate in question. If a large proportion of participants (>15%) have a missing covariate this may be imputed from other covariates. The imputation will be based on a mixed effect linear regression model developed for the highly correlated covariates. Multiple imputation approach will be used to account for uncertainty in missing values. If any value is missing at baseline, screening values may be used for imputation, if available.

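### If the 0.05 likelihood-ratio test for the cytokine response is taken from the PK/PD model that Section 6.2 selects on the same data, its type I error is not controlled

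*Combined protocol and SAP*

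**What the plan says.** Section 6.1 gives one significance level and one method for the cytokine response: it is to be assessed at days 5, 15 and 31 "at the 0.05 significance level using a log-likelihood ratio test and non-linear mixed effect regression modeling". The same paragraph claims "approximately 80% power to detect a 35% difference in plasma IL-6 levels between the disulfiram versus placebo groups". It adds that adjustment will be made for the pre-treatment level. It does not give the degrees of freedom of the test or its sidedness.

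Section 6.2 then describes how the primary pharmacodynamic response is modelled: "the PK and PD data will be combined and analyzed simultaneously by nonlinear mixed-effects modelling". On the drug-effect part it says: "Both empiric and mechanistic based pharmacodynamics models will be evaluated to describe the concentration effect relationship with the primary pharmacodynamics response". The choice among candidates is stated as "Model selection will be based on visual inspection of diagnostic scatter plots, the objective function value (OBJ) computed by NONMEM", with biological plausibility of the estimates as a third criterion. No candidate list, default form, numerical selection rule or allowance for selection is given.

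Section 6.2 also lists two arm comparisons that involve no such search. One is a GEE model with a two-sided Wald test. The other is a set of Wilcoxon rank-sum tests, named specifically for the inflammatory biomarkers, by day. The plan does not say which comparison is primary. The same section calls the study exploratory.

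**The concern.** NONMEM's objective function is minus twice the log-likelihood up to a constant. One of the quantities used to rank candidate models is therefore the quantity a likelihood-ratio test is built from. If several drug-effect forms are tried and the better-fitting one is kept, its drop in objective function is in effect the largest of several draws. Comparing that drop with the usual chi-square cut-off (3.84 on one degree of freedom) treats it as a single draw.

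This differs from the question of which test, cytokine, day or cohort is primary. If all of those were settled and the likelihood-ratio test were named as the sole primary test, the problem would remain, because the model inside the test would still be chosen from the data.

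With 20 against 10 participants per cohort, a spurious concentration-effect relation could be reported as a significant primary result. Section 6.2 also intends to use the final model to simulate other dosing schedules, so a false relation would carry forward.

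**Working it through.** **1. The plan's own power figure.** Inputs from Section 6.1: "Based on a mean plasma IL-6 level of 36.7 pg/mL (95% CI 21.6-62.3 pg/mL"), so a 35% difference is 0.35 × 36.7 = 12.845 pg/mL; and "the standard deviation of the pre- and post-dose levels is 12 ng/mL". I read the SD as 12 pg/mL to match the mean, which is an assumption. Section 5.3.4 gives the allocation: "randomized 2:1 to receive either disulfiram 2000 mg (N=20) or placebo (N=10) daily for 5 consecutive days".

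Standard error = 12 × √(1/10 + 1/20) = 4.648. Then 12.845/4.648 = 2.764, and 2.764 − 1.960 = 0.804, so power = Φ(0.804) = 78.9% (76.1% with a non-central t). The stated figure of about 80% is thus reproduced by a plain two-group comparison at one time point on the raw scale, with no model search in it. The plan does not show its calculation, so this match is an inference.

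**2. Simple bounds on best-of-k selection at the 3.84 cut-off, no true effect.**
- Independent candidates: 1 − 0.95^k = 14.3% for k = 3 and 26.5% for k = 6.
- Pairwise correlation 0.7, k = 3 to 8: 10.9% to 19.1%.
- Pairwise correlation 0.9, k = 3 to 8: 8.3% to 11.9%.
- Two fitted drug parameters tested as one: P(χ²₂ > 3.84) = e^(−1.92) = 14.7%.

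**3. Null simulation with exposure spread from Table 1.** Settings: days 5, 15 and 31; random intercept with known correlation (0.3 to 0.8); day effects; baseline adjustment not modelled; 1,500 to 4,000 runs per setting; Monte Carlo error about 0.4 to 0.7 points. The drug term with the largest likelihood-ratio statistic was tested against 3.84.

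| Candidate set (assumed) | One cohort, 20 v 10 | All 60 |
|---|---|---|
| 4 exposure metrics, one time course | 6.8-7.3% | 8.9-10.7% |
| 16 terms (4 metrics × 4 time courses) | 17.5-19.3% | 20.8-24.6% |
| 32 terms (adding an Emax grid) | 17.1-19.5% | 21.7-24.6% |

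One term fixed in advance gave 4.7-6.7%. For the 4- and 16-term sets, using the two-degree-of-freedom cut-off after selection gave 2.3-6.4%. A permutation test that repeated the whole automated search gave 4.1-5.6%.

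**4. Null simulation with baseline adjustment** (maximum likelihood, 20 v 10, correlation 0.3/0.5/0.7, 3,000 runs each).
- Fixed arm term: 7.1/6.8/6.2%.
- Best of three arm-effect time shapes: 14.9/15.6/13.7%.
- Best of six, adding exposure-driven forms with log-SD 0.5-0.6: 24.2/25.1/22.2%.

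**5. Sensitivity to exposure spread.** Table 1 (Section 4.1.7) gives 2.5 to 97.5 percentile ranges, so log-SD = ln(upper/lower)/(2 × 1.96).
- Parent, 1000 mg: ln(12,861/7,419)/3.92 = 0.14.
- Parent, 2000 mg: ln(35,102/18,482)/3.92 = 0.16.
- Across all analytes at the two trial doses: from ln(9,701/6,248)/3.92 = 0.11 to ln(14,886/4,974)/3.92 = 0.28.

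A rebuilt version of the simulation in step 4 (correlation 0.5) gave 23.5% for best of six at log-SD 0.5/0.6, and 17.7% at 0.14/0.28. Narrower sets gave less: three Day 5 forms (arm, parent, metabolite) 8.6%, and three constant forms 9.6%. A single fixed term gave 6.0%, so part of the excess over 5% is small-sample error in the chi-square reference, not selection.

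**The case against.** The strongest reply is that the plan never says the 0.05 test is taken from the selected PK/PD model. The likelihood-ratio test appears once, in the power paragraph. The uses stated for the PK/PD model are description, predictive checks and dose-schedule simulation. Section 6.2 already holds arm comparisons that selection cannot touch, and the study is labelled exploratory. All of this stands, and it makes the point conditional. It does not remove it. Section 6.1 ties its level and power to a likelihood-ratio test in non-linear mixed-effects modelling, and Section 6.2 describes no other such model for the cytokine. If another is meant, it has to be written down. An exploratory label sits comfortably with reporting the models without a p-value, but does not justify a 0.05 test after an open search.

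A reader might infer that the false-positive rate is about 14-25% instead of 5%. The documents do not support that as a property of the plan. It needs an assumed number of fairly distinct candidates and a one-degree-of-freedom cut-off the plan does not state. The upper end of the range in step 4 also uses an exposure spread wider than Table 1 implies. Against that, Table 1 is model-estimated, and Section 4.1.6 reports much wider raw concentration variability elsewhere.

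A reader might also infer that the chosen form is necessarily the one with the largest apparent drug effect. That does not follow. Plots and plausibility also count, and the objective function falls with a better time course or error model too. The simulations varied only the drug term and applied no plausibility screen, although Section 4.1 has over 90% of the drug gone within 3 days of a dose, which bears on an effect growing to Day 31.

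Finally, the text does not say that selection is done unblinded. It is implied only because drug concentrations separate the arms.

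**Conclusion.** The concern holds in conditional form. If the likelihood-ratio test of Section 6.1 is taken from the model chosen under Section 6.2, its type I error is not controlled, and the stated level and power do not describe it. In the settings examined, best-of-several selection at the one-degree-of-freedom cut-off gave about 7-25%. The low end belongs to a small, highly correlated set of forms and the high end to a rich set. Charging the selected shape as an extra degree of freedom brought the rate to 2.3-6.4%. The plan does not say this will be done, and switching between parent and metabolite exposure adds no parameter, so ordinary counting would miss that choice.

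These figures rest on assumed candidate sets, selection on likelihood alone and simple correlation structures. They show direction and rough scale, and are not an estimate for this trial. The matter should be settled in the SAP before unblinding.

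**What to change.** In Sections 6.1 and 6.2, take the 0.05 test from one arm comparison fixed before unblinding. A suitable choice is a linear mixed model of log cytokine on baseline, day and arm-by-day, with the tested contrast named (which day or combination of days, which cohort) and a small-sample reference distribution. Alternatively, name one of the selection-free comparisons already in Section 6.2 as the sole primary test, again with its day and cohort.

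Restate the power for whichever test is named, on the scale it uses. Report the NONMEM concentration-effect models as exploratory, without a significance claim.

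A re-randomization p-value that repeats the model search is not a ready substitute. Relabelled placebo participants have no drug concentrations, and visual selection cannot be repeated automatically. It would need a scripted selection rule and a stated rule for their exposure.

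The cost is SAP wording and one simple extra model. The small downside is that the PK/PD model no longer carries the p-value.
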